Patients ability of early ambulation will be evaluated using Timed Up and Go (TUG) test at 24 and 48 hours after surgery. To do the TUG test, patients will have to sit down on the bed, get up from the bed, walk 3 meters forward, turn, walk back 3 meters to the bed and sit down. The time taken by a patient to perform this test will be calculated with a chronometer. After the conversation with each patient and assessment of postoperative pain control efficacy, extent of motor blockade, ability of early ambulation, the rate of patient satisfaction will be evaluated using a 10 point scale from 0 to 10 at 3, 6, 24, 48 hours after surgery. The rate of complications (if any), including falls, local anesthetic toxicity or neurological complications, will be recorded in both groups of patients. According to study protocol, both groups of patients will be compared in terms of the extent of motor blockade postoperative pain control, ability of early ambulation, need for additional opioid analgesics, satisfaction rates over the time of clinical recovery.

Statistical Analysis Plan

The age, gender, BMI, ASA status will be collected.

The variable for power calculation analysis is the difference in motor blockade between the groups of patients. The difference in motor blockade of 30% would be clinically significant. To detect differences for a power of 90% and a 2-tailed α error of 0.05, a sample size of 33 patients per group would be required. However, due to possible missing data, 80 patients will be included in the study.

The statistical analysis will be performed using SPSS (version 25.0 IBM). The Kolmogorov-Smirnov test will be used to assess the normality of data distribution. For normally distributed numerical variables the Student t test will be used to compare means. Categorical variables will be compared using the Chi-squared test. A p value < 0.05 will be chosen as statistically significant.

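### Missing data are met only by enrolling 80 instead of 66, and the two named tests neither use the earlier scores of patients who miss a visit nor compare the arms jointly over 3 to 48 hours

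*Combined protocol and SAP*

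**What the plan says.** The Statistical Analysis Plan bases the sample size on motor blockade: "The variable for power calculation analysis is the difference in motor blockade between the groups of patients". It states that "a sample size of 33 patients per group would be required", then adds: "However, due to possible missing data, 80 patients will be included in the study". That sentence is its only mention of missing data. It gives no expected rate, assumed mechanism, analysis set, method of handling or sensitivity analysis.

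For numerical outcomes the plan says: "For normally distributed numerical variables the Student t test will be used to compare means". Categorical outcomes get the Chi-squared test. No time point is attached to either test, and no repeated-measures model or summary over time is named.

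Under Design and Methods in the Study Protocol, motor blockade (Bromage grades), VAS pain (at rest, on active flexion, on passive flexion) and satisfaction are each recorded at 3, 6, 24 and 48 hours. The Timed Up and Go (TUG) test is done at 24 and 48 hours. The same section ends by saying the groups will be compared on motor blockade, pain, ambulation, opioid need and "satisfaction rates over the time of clinical recovery".

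**The concern.** Extra patients restore precision. They do not make the patients who still have a score at 48 hours representative of their arm. With two-sample tests and no other method, the natural reading is that each visit is analysed on whoever has a value. A patient seen at 3, 6 and 24 hours but not at 48 then contributes nothing at 48 hours, although the earlier scores say something about the missing one.

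Suppose, for illustration, that patients with less pain at 24 hours are more often unassessed at 48 hours. The arm with less pain then loses more of its best patients, and the 48-hour difference shifts.

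A second issue does not depend on missing data. The protocol announces a comparison over recovery, but neither named test estimates an arm effect across visits or asks whether that effect changes with time.

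**Working it through.** **1. The margin.** From the Statistical Analysis Plan: 2 × 33 = 66 needed and 80 enrolled, so 80 − 66 = 14 extra and 14/80 = 17.5%. Check: 66/(1 − 0.175) = 80. The number 80 also results from 66 × 1.2 = 79.2 rounded up, so the intended rate cannot be read back from it. The 33 per group cannot be verified either, because no SD or control rate is given. A standardised difference of 0.8 would produce it, but nothing below depends on that.

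**2. Bias in a visit-by-visit comparison.** The documents give no SD, correlation or loss pattern, so all inputs here are assumptions:
- 40 patients per arm; VAS SD 2; mean difference 1 point at both 24 and 48 hours (24-hour means 4 and 3);
- correlation ρ between the two visits of 0.3, 0.5 or 0.7;
- the same loss mechanism in both arms: logit P(missing at 48 h) = −2 − b × (VAS at 24 h − 3.5);
- 4,000 simulated trials per cell.

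| Loss scenario | Lost per arm | Available-case 48 h difference, ρ = 0.3 / 0.5 / 0.7 | Shortfall from 1 |
|---|---|---|---|
| b = 0.5 | 12.8% and 18.6% | 0.97 / 0.95 / 0.93 | 0.03 / 0.05 / 0.07 |
| b = 1 | 17.3% and 28.5% | 0.92 / 0.87 / 0.82 | 0.08 / 0.13 / 0.18 |

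Repeat runs moved individual entries by about 0.01, hence the range 0.03 to 0.08 for the first row. Average loss is (12.8 + 18.6)/2 = 15.7% in the first row, within the margin, and (17.3 + 28.5)/2 = 22.9% in the second, beyond it.

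A likelihood estimate that uses the 24-hour score gives 0.99 to 1.01 in every cell, with a standard error within 3% of that of the t test.

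**3. Why the numbers behave this way.** With equal SDs, bias at 48 hours = ρ × (change in the 24-hour arm difference among patients still observed). In the heavier scenario that change is 0.08/0.3 ≈ 0.13/0.5 ≈ 0.18/0.7 ≈ 0.26 points at each ρ. The true 48-hour difference does not enter. So if the arms differ by 1 point at 24 hours but not at all at 48 hours, the same mechanism produces a spurious 48-hour difference of about 0.7 × 0.26 = 0.18 points, in the opposite direction to the 24-hour difference.

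**4. Check with another mechanism.** Here loss at 48 hours depends on the 6-hour score (logistic slope 1.5), ρ is 0.3 to 0.7, and the 6-hour arm difference is 0.8 SD or zero.
- Same mechanism in both arms, arms differ at 6 hours, 17.5% lost overall: bias −0.04 to −0.10 SD.
- Loss depends on the score in one arm only (17.5% lost in one arm, about 24% in the other): −0.08 to −0.19 SD.
- Loss depends on the score in one arm only, no arm difference at 6 hours: −0.06 to −0.14 SD.
- Same mechanism, no arm difference at 6 hours: about 0.

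Using the earlier score recovers the true difference to within 0.005 SD throughout.

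**5. Motor blockade, extreme bounds.** Treat it as a yes/no outcome with an observed difference of 30 percentage points and 17.5% missing in each arm. If all the missing in one arm had the event and none in the other, the difference would be 0.825 × 30 ± 17.5 = 24.75 ± 17.5, or 7.25 to 42.25 points.

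**The case against.** The strongest reply is that the plan does not say what is being criticised. No sentence limits the t test to one visit or to patients with a value there; strictly, the handling is unspecified. That stands, so the point is put as what the named tests imply.

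Nor do the documents supply a loss mechanism. There is no discharge rule, and the TUG test at 48 hours starts and ends at the bed, which suggests patients are still within reach. A reader might infer from the margin that the sponsor expects to lose 14 patients, but the text speaks only of possible missing data. Both limits stand.

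The size is also small. At a loss within the margin, 0.08 points against a standard error of about 0.47 to 0.49 is at most about 0.16 standard errors. That stands too. It does not follow that the error can only dilute a real difference: steps 3 and 4 show a false difference at 48 hours when the arms differed earlier, or when the mechanism differs by arm.

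The phrase about recovery could mean no more than a comparison at each scheduled assessment, and no listed objective asks for an arm-by-time test. That reading is open, so the lack of a joint comparison is a weakness and not a contradiction.

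Finally, 7 to 42 points might be taken as the likely error in the motor blockade result. It is not: any trial with 17.5% missing has bounds that wide, a mixed model would not narrow them, and the protocol records Bromage grades, not a yes/no outcome.

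**Conclusion.** The point holds in a conditional and modest form. Over-enrolment is the only provision for missing data, and neither named test uses earlier scores or compares the arms jointly over recovery.

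Bias arises only if loss depends on earlier scores and the arms differ on them, or if the loss mechanism differs by arm. Under the assumed inputs of step 2 it is 0.03 to 0.08 VAS points at 13–19% loss per arm, and 0.08 to 0.18 at 17–29%. It vanishes if loss is unrelated to scores, or if the arms do not differ and share one mechanism.

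The documents do not support the stronger conclusion that the later comparisons will be biased: they give neither a loss rate nor a mechanism, and 48 hours of follow-up may keep loss low. The change is still worth making, because the better analysis loses almost no precision and supplies the joint comparison.

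**What to change.** Amend the Statistical Analysis Plan before unblinded data are seen:

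- **VAS at rest, on active flexion and on passive flexion, and satisfaction.** Replace the separate t tests by one linear mixed model per outcome in SPSS MIXED: arm, time as a category, arm-by-time, unstructured within-patient covariance, all randomised patients with any score. Report the arm difference with its confidence interval at each visit, and the arm-by-time test.
- **VAS on active flexion and TUG.** A value missing because the patient could not perform the task is not an ordinary missing value. Record the reason, report the number unable by arm, and interpret the means with that in view.
- **Motor blockade.** State the grade and time point that define the outcome, and add a best/worst-case table for missing patients, labelled as a sensitivity bound and not as an estimate of bias. This table does not provide an over-time comparison for motor blockade.
- **Missing data.** State the assumption made, and report the number with a value by arm and visit.

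The cost is SAP wording and four SPSS MIXED runs, with no extra patients or visits. The downside is a slightly more complex analysis that assumes loss is explained by the observed scores.
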